4.2 Design for Viral Suppression

The viral suppression component of the study is a two-arm, site-randomized, prospective, effectiveness clinical trial. It will be conducted within each intervention community to assess the effectiveness of a FI intervention for achieving and maintaining suppressed VL (HIV RNA < 400 copies/mL) in HIV-positive individuals (who have initiated ART under prevailing guidelines) compared to SOC for supporting patients in achieving adherence and virologic suppression. Each HIV care site will be randomized to either the intervention or SOC arm of the study. For this component of the trial, study outcomes will be evaluated through routinely reported HIV surveillance data. Using surveillance data, study outcomes will continue to be evaluated for a period of one year after the FI intervention ends.

In order to identify the SOC for ART adherence/viral suppression support, against which the incentives intervention will be assessed, we will develop a brief survey to be completed by an appropriate facility administrator, which will collect key attributes of HIV care sites, including types of ART adherence support, case management services, and other support services already available to patients. Data will be collected from sites annually from 2009 - 2013.

4.3 Study Population for Viral Suppression

The study population for the viral suppression component of the study will include all individuals ages 12 and older who are permitted to consent, or can be consented for HIV care by a parent/legal guardian according to New York State or Washington, D.C. law, who have initiated care at participating HIV care sites.

4.4 Study Sites for Viral Suppression

Twenty HIV care sites will be selected from Washington, D.C. and 20 HIV care sites will be selected from the Bronx to participate in this component of the study. Sites will be selected based on two primary criteria: 1) site agreement to participate in this component of the study, and 2) sites with the highest number of HIV-positive patients in care in the previous year. Additional site selection criteria may be considered if a total of 40 HIV care sites cannot be chosen based on the primary criteria.

HIV care sites will be randomized 1:1 to the FI vs. SOC, stratified by city and balanced by size of patient population in a clinic and baseline levels of proportion of VL showing suppression. In each city, these 20 sites will be randomized such that 10 will use the FI intervention, described in Section 4.5, to promote viral suppression in HIV-patients on ART and 10 will continue the existing SOC.

The site randomization will be balanced by the following two baseline characteristics:

• The size of the site's HIV-positive patient case load

• The proportion of HIV-positive patients with VL suppression at each site

4.5 Intervention for Viral Suppression

HIV-positive individuals at HIV care sites assigned to the FI intervention will receive FIs (gift cards worth \$70) to reinforce adherence to ART as measured by confirmation of each suppressed VL measurement (<400 copies/mL). The gift cards will be distributed at the HIV Care sites during each routine, quarterly clinic visit that a study participant demonstrates a suppressed VL.

In the event participants report full adherence to their providers but have not succeeded in achieving VL suppression, providers will be expected to obtain resistance testing, as recommended by current treatment guidelines, and to alter their patients' regimens accordingly. Once patients with resistant HIV are on appropriate regimens, they will again be eligible for FIs for viral suppression. The specific procedures for HIV care sites to distribute the FIs for viral suppression will be outlined in the HPTN 065 SSP.

This intervention will be compared to SOC support for ART adherence through the use of routinely collected HIV surveillance data.

4.6 Study Procedures for Viral Suppression

At the initiation of the study, the study team, along with experts in treatment and management of HIV disease, will provide training to providers in the intervention communities on current HIV-treatment guidelines. Training will encourage providers to maximize initiation of ART per current guidelines and will emphasize the following: eligibility criteria for ART as defined in the guidelines; assessment of patient readiness to start ART (if eligible); prompt initiation of ART (if eligible); use of recommended regimens; the provision of supportive services to ensure adherence; regular clinical and laboratory monitoring; the importance of assessment for evidence of treatment failure; reinforcement of adherence; obtaining HIV resistance testing (if appropriate); and modification of failing regimen with new effective regimen. All HIV care site staff will also be trained on the procedures for the FI intervention prior to implementation. Along with this training, the importance of linkage to supportive services will be emphasized, including income assistance, housing support, substance use management and mental health services. Each HIV care site, regardless of the study arm it is randomized to, will be provided with a listing of available resources in the community with contact names and numbers. Providers will also be trained on HIV prevention counseling.

A baseline survey will be conducted to determine the availability of supportive services at all participating HIV care sites (*e.g.* social services, adherence support, substance use treatment, support groups, mental health resources, *etc.*) and to determine whether these services are available on site or by referral. In addition, an effort will be made to monitor the number of new referrals and waiting times for appointments to assess program capacity.

The specific procedures for HIV care sites to distribute the FIs for viral suppression will be outlined in the HPTN 065 SSP.

4.6.1 Monitoring HIV Care Sites

It is possible that members of the intervention communities, particularly those who are HIV-positive, will learn of the FI intervention to promote viral suppression and seek out HIV care sites offering these incentives. In an effort to minimize significant migration of patients from HIV care sites without FIs to ones that offer them, the following rules have been put into place:

- A patient must have at least one VL measurement at the HIV care site between three and nine months prior to the first suppressed VL for which he or she may receive an incentive. Both of these VL measurements must be done at the same HIV care site.
- All subsequent VL measurements for which a patient may receive FIs must be performed at the same HIV care site.

If a patient changes HIV care sites during the course of the study, he or she will be required to "establish care" at the new HIV care site prior to receiving any FI for a suppressed VL as indicated above. Specifically, to receive an FI again, the individual must have a VL measurement at the new HIV care site and return in three to nine months for a repeat VL measurement. The results of the second test will determine whether the person receives the FI or not.

Despite this barrier to HIV-care-site migration, the FI intervention may encourage this phenomenon; thus, the study team will use surveillance data to monitor the case load at each site at frequent intervals. By monitoring HIV care site case load over time, the team will be able to determine if significant migration is taking place. This will motivate discussions with the community advisory group to design other mechanisms to minimize such migration or if needed a redesign of this component of the study may be embarked on by the study team.

4.7 Study Duration for Viral Suppression

The duration for the FI intervention for the viral suppression component of the study is depicted in Figure 3. Participants will be eligible to receive FIs for suppressed (< 400 copies/mL) VL measurements once every three months throughout the entire 24-month study period. Participants who miss a quarterly visit(s) remain eligible for incentives as long as they present back to care with a suppressed VL measurement.

Patients with HIV diagnoses returning to care after a hiatus (of at least a year) and individuals who switch HIV care sites during the study are all eligible for the FIs. However they must have at least one VL measurement at three months (or more) at the same HIV care site as the qualifying VL measurement for which they can receive an FI.

Accrual of participants into the Viral Suppression component of the study will occur over the entire 24 months of the study. Some participants may receive up to nine FI payments if they are seen at the same HIV care site throughout the entire study, had been receiving care at that the same site before the study began, and maintain viral suppression throughout the 24 months.

Figure 3: Duration of FI Intervention for Viral Suppression

4.8 Statistics and Data Analysis for Viral Suppression

4.8.1 Endpoints

4.8.1.1 Endpoints for the feasibility of using financial incentives in the HIV-positive population for viral suppression

The feasibility endpoints for the viral suppression component of the study will include the following:

- Number of individuals eligible for incentives and receiving incentives at a select subset of sites for select time points
- Cost of program including staffing, infrastructure and incentives

4.8.1.2 Endpoints for the Effectiveness of Viral Suppression

The effectiveness endpoints for the viral suppression component of the study will include comparing between sites in the intervention and SOC arms:

- Probability of an HIV-positive patient in care at a site having a suppressed VL (<400 copies/mL) in the 12-month calendar assessment period beginning 12 months after initiation of the assessment period
- Number of identified HIV-positive patients in care who have sustained viral suppression (see below)

The primary endpoint of the intervention is evaluated using all VL ordered at each site in the 12-month period beginning 12 months after initiation of FIs. An individual will be defined as in care at a site if two VL or CD4 assessments were ordered at that site in the year prior to initiation of this study, or if care (defined by two VL/CD4 assessments) is initiated at the site during the study. PLWHA will be assigned to sites (and thus arms) based on the site where they are in care.

To avoid ascertainment bias that would arise from missing VL assessments in the in-care cohort, we will impute whether VL is suppressed in each quarter of the 12-month assessment period a patient is in care (this is based on an SOC where VL assessments are ordered approximately every three months). For example, a patient with a VL assessment in each quarter will have an endpoint assessment for each quarter. A patient who has a suppressed VL assessment in the first, third and fifth quarters, but no assessment in the second and fourth, will be assumed to be suppressed in the second and fourth. However a patient with a suppressed VL in the first quarter and no subsequent assessment throughout the study will be assumed not suppressed in all subsequent quarters. The algorithm for imputing VL suppression (incorporating the sequence of VL assessments and including management of the reporting lag in surveillance data), inclusion of assessments in the quarters preceding and following the assessment period, handling of cases in treatment at more that one site, and censoring because of moving outside the surveillance area, death, etc. will be detailed in the statistical analysis plan. Contamination between arms will be tracked by detection of patients with VL assessments at multiple providers in the year.

It should be noted that the existing surveillance procedures include extensive efforts to link cases across jurisdictions. Individuals moving outside the jurisdiction will be censored at last measure prior to relocation.

4.8.3 Randomization Scheme

In the viral suppression study component, facilities that provide HIV care services (HIV care sites) will be randomized to use FIs or the SOC.

HIV care sites will be assigned to one of the following two arms:

- Sites offering FIs for VL suppression: FIs offered to all those who are on ART, upon the confirmation of each suppressed VL measurement (<400 copies/mL)
- Sites continuing with SOC to encourage VL suppression: Each person on ART will be offered support via the site's SOC procedures to attend HIV care site visits and remain adherent to their ART regimen in order to achieve and maintain VL suppression

The site randomization will be balanced by the following two baseline characteristics:

- The size of the site's HIV-positive patient case load
- The proportion of HIV-positive patients with VL suppression at each site

4.8.4 Data Analysis

Data to be analyzed for this study component will be obtained from routine HIV surveillance data as well as from the participating sites. Participating sites will maintain tracking logs for FIs provided to participants maintaining suppressed VLs. Information from the tracking logs, with all participant-identifying information removed, will be provided to the study team.

The data for the effectiveness of an FI intervention for high ART adherence to achieve viral suppression compared to the SOC will be analyzed as described below. Analysis of secondary endpoints will be detailed in the statistical analysis plan.

4.8.4.1 Primary Effectiveness Analysis

The assessment cohort includes all HIV cases identified from HIV surveillance in the intervention city DOH jurisdiction that have a VL assessment in the 24 months of trial duration. The assessment period for each site begins 12 months after the onset of FIs in each city. An intention-to-treat approach will be used to assign patients to the care site assignment existing at the trial onset. For the 12-month assessment period (*i.e.* from 12 through 24 months), all VLs in the surveillance data assessed by the 40 clinics in the study are used to assess differences in percent achieving viral suppression by study arm. Details about each site's contribution of patients who enter into care during the study will be provided in the statistical analysis plan. As described in 4.8.1.2, an imputation scheme for assessing VL suppression during the 12 months of the assessment that avoids the bias of missing assessments will be applied to all patients in care.
The estimate of intervention effect is the odds ratio of VL suppression in the FI intervention compared to SOC arms, assuming both a within-person and within-clinic correlation, stratified by city, using GEE methods. Sensitivity analysis will be conducted to assess the impact of patients who switch providers or establish care at multiple providers during the trial.

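### Viral-suppression primary analysis: arm, cohort membership and outcome can each depend on clinic attendance after randomisation, which exposes the comparison to bias of unknown size and direction

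*Protocol*

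**What the plan says.** Three rules for the primary analysis matter here.

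- **Arm.** Section 4.8.4.1: "An intention-to-treat approach will be used to assign patients to the care site assignment existing at the trial onset". Section 4.8.1.2: "PLWHA will be assigned to sites (and thus arms) based on the site where they are in care". In that section a person is in care at a site through two VL or CD4 results there in the year before the study, "or if care (defined by two VL/CD4 assessments) is initiated at the site during the study".
- **Outcome.** Section 4.8.4.1: "all VLs in the surveillance data assessed by the 40 clinics in the study are used to assess differences in percent achieving viral suppression". Section 4.8.1.2 imputes missing quarters; in its example, a patient with one early suppressed VL and "no subsequent assessment throughout the study will be assumed not suppressed in all subsequent quarters". Censoring is planned for death and for leaving the surveillance area.
- **Cohort.** Section 4.8.4.1 takes surveillance cases "that have a VL assessment in the 24 months of trial duration".

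Section 4.6.1 ties payment to place: the qualifying pair of VLs must come from one site, and "All subsequent VL measurements for which a patient may receive FIs must be performed at the same HIV care site". It accepts that incentives may prompt patients to change sites. Section 4.1 makes moves from non-intervention to intervention sites a feasibility measure.

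The imputation algorithm, patients treated at several sites, and the contribution of patients who enter care during the study are left to the SAP, which is not at hand.

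**The concern.** Randomising clinics protects the comparison only if who is analysed, in which arm, and how the outcome is read do not depend on what patients do after the incentives start. Here each depends in part on attendance that one arm is paid for. The odds ratio could then mix a true effect on suppression with loyalty to a study clinic, movement between arms and return to testing. The planned increase is 6 points (60% to 66%, Section 4.8.2), so a distortion of a few points would matter.

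**Working it through.** **Yardstick.** Section 4.8.2 claims 90% power for 60% against 66% with 20 clinics per arm and 219 patients per clinic (Table 3: SDs 16% and 15%). Alpha is not stated for this component; two-sided 5% is assumed. By the Hayes-Bennett formula, the variance per clinic pair is 0.24/219 + 0.2244/219 + 0.16² + 0.15² = 0.0502. The standard error is √(0.0502/19) = 0.0514, and power is Φ(0.06/0.0514 − 1.96), about 21%. The 90% is not reproduced. That is a separate problem; only the 6-point target is used below.

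**(a) Arm rule.** Where patients fall:

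| Patient | Section 4.8.4.1 | Section 4.8.1.2 |
|---|---|---|
| Baseline SOC patient who stays | SOC | SOC |
| Baseline SOC patient who establishes care at an FI site | SOC | qualifies at both sites |
| First enters care during the study at an FI site | no onset site | FI |

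Take no true effect, 60% suppressed in both arms, and x suppressed patients per 100 moving from SOC to FI (assumed). If movers count where they are now in care, the difference is (60 + x)/(100 + x) − (60 − x)/(100 − x).

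- x = 2: 62/102 − 58/98 = 60.8% − 59.2% = 1.6 points.
- x = 5: 65/105 − 55/95 = 61.9% − 57.9% = 4.0 points.
- If only 80% of movers are suppressed: 0.8 and 2.0 points.

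Under the onset rule the difference is 0 in every case.

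**(b) VL source.** Take a transfer to a non-study clinic in the jurisdiction. Under the 40-clinic rule the new VLs are not used; the missing-VL rule then scores the later quarters as unsuppressed; censoring does not apply, because the patient is alive and in the area. For patients away for the whole assessment period, the false difference is 0.60 × (SOC leaving rate − FI leaving rate).

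- 6% against 3%: 0.60 × 0.03 = 1.8 points.
- 10% against 5%: 0.60 × 0.05 = 3.0 points.
- A wider range of excess SOC leaving, 2 to 10 points: 1.2 to 6.0 points.
- If leavers lose two of the four quarters, halve these: 1.8 to 3.0 becomes 0.9 to 1.5.

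The leaving rates are assumptions. As an indication that care outside the study clinics exists, the Schema projects about 30,000 people in care in the two communities, while Section 4.8.2 puts about 5,000 + 16,000 = 21,000 at the top 20 sites in each. The periods differ, so this gives no leaving rate.

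**(c) VL required in the 24 months.** A baseline in-care patient with no VL during the trial is outside the Section 4.8.4.1 cohort, yet under the missing-VL rule would count as not suppressed. Suppose each arm has 100 patients who return anyway, 60 of them suppressed, and 5 who return only if paid, of whom 2 become suppressed (assumed).

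- As written: FI 62/105 = 59.0%, SOC 60/100 = 60.0%; difference −1.0 point.
- Everyone kept: FI 62/105 = 59.0%, SOC 60/105 = 57.1%; difference +1.9 points.

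So this rule can hide a benefit of the incentive.

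**The case against.** The strongest reply is that much of this is left to the SAP, and that Section 4.8.4.1, the section that defines the primary analysis, names intention to treat by onset site. The in-care sentence in Section 4.8.1.2 could then be meant only for new patients, and a sensitivity analysis for switchers makes most sense if the primary analysis does not reassign them. This is a fair reading, and the two rules agree for baseline patients who never move. But neither section says which rule governs movers, and the onset rule gives newcomers no site. The deferrals do not cover the VL source, the VL-in-24-months requirement or the onset rule itself.

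It can also be said that the missing-VL rule does not mention study clinics, so scoring a transferred patient as a failure is an inference. That is true: it follows only when the rule is read with the 40-clinic restriction. The switcher sensitivity analysis might bring in VLs from other clinics; its method is not given.

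A reader might go further than the documents allow:

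- **That the comparison is biased, in favour of FI.** No switching, leaving or return rate is given. Mechanism (b) plausibly favours FI; (c) may work against it.
- **That suppressed newcomers are selected into FI sites because the second VL can earn $70.** Two VL or CD4 results of any value qualify. Suppose SOC sites include 80% of suppressed and 60% of unsuppressed patients (assumed). Ten points more inclusion of suppressed patients at FI sites gives 0.54/0.78 − 0.48/0.72 = +2.6 points; ten points more of unsuppressed patients gives 0.48/0.76 − 0.48/0.72 = −3.5 points.
- **That only VLs from a patient's own clinic count.** Section 4.8.4.1 accepts any of the 40 clinics, and its cohort needs a VL anywhere in the jurisdiction. Same-site testing governs only payment and entry as a newcomer.

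**Conclusion.** The point holds as exposure to bias of unknown size and direction. Two sections of the protocol must be reconciled on the arm rule, and the VL source and cohort rule, as written, let behaviour after randomisation shape the result. Illustrative effects are 1.6 to 4.0 points from 2 to 5 suppressed movers per 100 under the in-care rule, 1.8 to 3.0 points from differential leaving, and a shift in the other direction from dropping patients who never return. All rest on assumed rates and, for the first two, on 60% suppression in both arms. They are large enough against 6 points to justify settling the rules before data are seen; they do not show that the result will be wrong.

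**What to change.** For patients who meet the pre-study in-care definition:

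1. Assign each to that site and arm throughout, whether or not a later VL exists.
2. Take each quarter's VL from any provider in the jurisdiction's surveillance data.
3. Score missing as unsuppressed only when no provider reported a VL, keeping the planned censoring for death and leaving the area.

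Limit the in-care-site rule to patients who first enter care during the study, assign them to their entry site, and report results with and without them. Whether they stay in the primary analysis is the sponsor's choice, because Section 4.3 includes all who have initiated care at participating sites. Report the analysis restricted to VLs from the 40 clinics as a sensitivity analysis.

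**Cost.** Protocol and SAP wording and some analysis work. Sections 1.1.8 and 7.2 say that both jurisdictions require reporting of all VL and CD4 results, so no new collection is needed. Fixed assignment dilutes a true effect: if 2%, 5% or 10% of SOC patients cross to FI sites and gain all of it, 6 points becomes 6 × 0.98 = 5.9, 6 × 0.95 = 5.7 or 6 × 0.90 = 5.4. Leaving newcomers out would cost little precision: a 25% smaller clinic (219 to 164, assumed) raises the variance above from 0.0502 to 0.4644/164 + 0.0481 = 0.0509, under 2%.

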4.8.4.2 Feasibility Endpoints

Descriptive statistics will be used to summarize the mean uptake and overall cost of FIs and its variation between sites by site and population characteristics.

